6.11.2 Physical Examination

In addition to the baseline complete physical examination, physical examinations will be performed and be summarized descriptively for Part A, open-label extension of Part A, and Part B at each scheduled visit and timepoint collected (screening, Visit 1, Month 3, Month 6, Month 9, Month 12, Month 15, Month 18, Month 21, Month 24, and every 6 months thereafter until recurrence or end of study).

6.11.3 Autoimmune Monitoring

Autoimmune monitoring will be performed and be summarized descriptively for Part A, open-label extension of Part A, and Part B (Safety Population) at each scheduled visit and timepoint collected (screening, Week 0, Month 6, Month 12, Month 18 and Month 24). For laboratory measures mean and mean change from baseline values will be presented for each timepoint collected. Change from baseline will be calculated as the post-baseline measurement minus the baseline measurement. If either the baseline or post-baseline value is missing, the observation will not be included in the change from baseline summary. Results from eye and skin exams will be listed.

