4.2 Exclusion Criteria

Subject must not meet any of the following exclusion criteria to be enrolled in the study:

1. Any prior melanoma treatment other than surgery or regional irradiation (irradiation must be completed more than 2 weeks prior to first dose of study drug), including adjuvant or neoadjuvant treatment. (Subjects who received interferon alfa-2b with adjuvant treatment intent, but discontinued within 1 week of starting treatment, at least 60 days before first dose of study drug, will be allowed to enroll)
2. Subjects who have a history of another malignancy within the past 5 years with the exception of adequately treated in situ squamous cell carcinoma, basal cell carcinoma, stage I or IIA melanoma, or carcinoma in situ of the cervix. See treatment exclusions noted within the other exclusion criteria.
3. Use of biologic response modifiers (e.g., interleukin-2, colony-stimulating factors, other cytokines, BCG) within 60 days prior to first seviprotilimut-L or placebo dosing.
4. Chronic use of systemic corticosteroids (other than inhaled or nasal steroids) or other immunosuppressants, or subjects expected to require acute systemic steroids (Medrol dose pack or other oral steroids) during the 24-month treatment course.
5. Known allergy to alum.
6. Use of any investigational agents within 30 days prior to first seviprotilimut-L or placebo dosing.
7. History of any chronic medical or psychiatric condition or laboratory abnormality that, in the judgment of the investigator, may contraindicate study participation or study drug administration or may interfere with the interpretation of study results.
8. Any kind of disorder that compromises the ability of the subject to give written informed consent and/or comply with the study procedures.
9. Prior splenectomy.
10. Known positivity for human immunodeficiency virus (HIV).
11. Participants must not have or had prior autoimmune disorders requiring cytotoxic or immunosuppressive therapy, or autoimmune disorders with visceral involvement. The following will not be exclusionary:
 - The presence of laboratory evidence of autoimmune disease without associated symptoms unless attending physician feels such symptoms are likely to arise within ninety (90) days of laboratory evidence.
 - Clinical evidence of vitiligo.
 - Other forms of depigmenting illness.
 - Mild arthritis requiring NSAID medications or no medical therapy.

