10.4 Autoimmune Monitoring

Autoimmune monitoring will occur through laboratory measurements of ANA and ESR. Other tests, such as RF, TSH, and T4, may be performed as clinically indicated. Furthermore, periodic physical examinations, including eye exam (performed by an ophthalmologist) and skin exam for vitiligo and rashes will be performed.

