6.0 STATISTICAL ANALYSIS

Categorical variables will be summarized using counts and percentages. Percentages are based on the number of patients in the analysis set for whom there are non-missing data, unless otherwise specified.

Continuous variables, including change from baseline, will be summarized using descriptive statistics [n, mean, standard deviation (SD), minimum, median, maximum].

The rates of binary endpoints will be compared using a one-sided Pearson χ^2 test for unstratified analyses and Cochran-Mantel-Haenszel (CMH) test for stratified analyses. For the unstratified analyses, point estimates of the rates for each treatment arm and difference of the rates between treatment arms will be provided along with the corresponding 2-sided 95% confidence intervals using an exact method based on the F distribution and using a normal approximation for constructing a confidence interval for differences, respectively. For the stratified analyses, the relative risk ratio estimator will be used to contrast the treatment effects on the endpoint. Both a point estimate and a 2-sided 95% confidence interval will be calculated using a normal approximation.

Time-to-event endpoints will be summarized using the Kaplan-Meier method and displayed graphically when appropriate. Median event times and 2-sided 95% confidence interval for each median will be provided. Cox proportional hazard models will be used to explore the potential influences of the baseline stratification factor on time-to-event endpoints. The estimated hazard ratio and 2-sided 95% confidence interval will be provided.

Stratified analyses will be conducted controlling for the randomization stratification variables of disease state (IIB/IIC vs. IIIA vs. IIIB/IIIC).

Baseline is defined as the last data point prior to randomization in Part A or Part B of the study, unless otherwise stated. Baseline is defined as the last data point prior to dosing in the open-label extension of Part A, unless otherwise stated.

Patient data listings will include all enrolled or randomized patients as applicable to Part A, open-label extension of Part A, or Part B of the study. Listings will be presented by or include part of the study where appropriate, and be sorted by treatment group, site, patient number, and date (if applicable).

Statistical analyses will be carried out using SAS statistical analysis software version 9.1.3 or higher (SAS Institute, Inc., Cary, North Carolina, USA).

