6.11.4 Laboratory Parameters

Clinical laboratory parameters for LDH, CBC, serum chemistry and urinalysis will be summarized descriptively for Part A, open-label extension of Part A, and Part B (Safety Population). Mean and Draft v3.2 (25 May 2016)

mean change from baseline values will be presented at each study visit. Change from baseline will be calculated as the post-baseline measurement minus the baseline measurement. If either the baseline or post-baseline value is missing, the observation will not be included in the change from baseline summary.

Each laboratory result will be classified as low (L), normal (N), and high (H) at each visit according to the laboratory-supplied normal range. The shift from baseline will be presented for each post-baseline visit for Part A, open-label extension of Part A, and Part B. In addition, for Part B, toxicity grade of lab result will be presented in a shift table for each post-baseline visit for the change from baseline.

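### SAP 6.11.3 summarises ANA only by mean and mean change from baseline, so its text specifies no count of baseline-negative patients who become ANA-positive

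*SAP*

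**What the plan says.** Protocol 10.4 states that "Autoimmune monitoring will occur through laboratory measurements of ANA and ESR". It adds that "Other tests, such as RF, TSH, and T4, may be performed as clinically indicated", so ANA and ESR are the only routine autoimmune laboratory tests. Protocol 5.1 places both at screening, and Protocol 5.2.6 repeats them at Months 6, 12, 18 and 24.

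For analysis, SAP 6.11.3 says: "For laboratory measures mean and mean change from baseline values will be presented for each timepoint collected". It defines the change arithmetically: "Change from baseline will be calculated as the post-baseline measurement minus the baseline measurement". It makes no exception for ANA and names no positivity count, titre category, log scale or shift table. Only the eye and skin results are treated differently; they are listed.

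SAP 6.11.4 does provide shift tables, but its scope is set by its first sentence: "Clinical laboratory parameters for LDH, CBC, serum chemistry and urinalysis will be summarized descriptively". SAP 6.0 has a general rule: "Categorical variables will be summarized using counts and percentages".

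On eligibility, exclusion 11 in Protocol 4.2 lists findings that do not exclude a patient. One is "The presence of laboratory evidence of autoimmune disease without associated symptoms", subject to the physician's view of whether symptoms are likely within 90 days. Patients who are ANA-positive at entry can therefore be enrolled.

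**The concern.** Induced autoimmunity is a risk that this trial monitors on purpose, with two laboratory markers and with eye and skin examinations. For ANA, the natural safety question is how many patients who were negative at baseline became positive, and whether that differs by arm.

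A mean change over all patients does not answer it. The measure mixes three groups: new conversions, changes of titre in patients already positive, and reversions to negative. If titres are averaged on the arithmetic scale, one or two high values can outweigh many low-titre conversions. The SAP's general laboratory section offers the better format (classification and shift from baseline), but its list leaves ANA out. At stake is whether the safety report shows an excess of asymptomatic seroconversions, if there is one.

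**Working it through.** The plan gives no ANA figure (no scale, cut-off, expected rate or precision), so there is nothing to reproduce. The check takes each plausible scale in turn.

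**Inputs from the documents.** Part B1 has 325 patients randomized 2:1: 325 × 2/3 ≈ 217 vaccine and 325/3 ≈ 108 placebo. Part B2 has 800 randomized 1:1: 400 per arm. Change is post-baseline minus baseline (SAP 6.11.3).

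**Inputs assumed.** Titres run from 1:80 to 1:2560. A negative result is coded 0 or 20. Seroconversion rates are as in the table below.

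**Scale 1: positive/negative.** Coded 0/1, with c conversions and r reversions among n patients, the mean change is (c − r)/n. This nets reversions against conversions and does not isolate c among the baseline-negative patients. If the results are not coded numerically, a mean is undefined. Either way, 6.11.3 asks for a mean where SAP 6.0 asks for counts and percentages.

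**Scale 2: titre, counterexample at B1 sizes.** All patients are negative at baseline. On vaccine, 22 of 217 convert to 1:80. On placebo, 2 of 108 convert, one to 1:80 and one to 1:2560.

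- Proportion converting: 22/217 = 10.1% against 2/108 = 1.9%. Vaccine is higher.
- Mean change, negatives coded 0: 22 × 80/217 = 8.1 against (2560 + 80)/108 = 24.4. Placebo looks about 3 times higher.
- Mean change, negatives coded 20: 22 × 60/217 = 6.1 against (2540 + 60)/108 = 24.1. Placebo looks about 4 times higher.
- Mean log2 change, negatives set to 20: 22 × 2/217 = 0.20 against (7 + 2)/108 = 0.08. Vaccine is higher, so the reversal comes from the arithmetic scale.

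**Patients positive at baseline.** One patient moving a single dilution, from 1:1280 to 1:2560, adds 1280 to the arm's total. That equals 1280/80 = 16 conversions from 0 to 1:80, or 1280/60 ≈ 21 if negatives are coded 20.

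**How often the order reverses.** The simulation used 20,000 replicates per scenario, with all patients baseline-negative and negatives coded 0. Converters' titres were spread over 1:80 to 1:2560 with three weightings (halving, dividing by three, flat). The vaccine rate is always the higher one. Each range below is across the three weightings.

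| Arms | True rates (vaccine v placebo) | Mean change misranks | Proportion misranks | Mean wrong, proportion right |
|---|---|---|---|---|
| 217 v 108 | 10% v 5% | 12.2–16.5% | 5.1–5.3% | 9.1–13.6% |
| 217 v 108 | 10% v 2% | 1.4–3.9% | 0.1% | 1.3–3.8% |
| 217 v 108 | 15% v 5% | 2.0–5.6% | 0.1–0.2% | 1.9–5.5% |
| 217 v 108 | 6% v 3% | 16.6–19.0% | 11.2–11.4% | 9.5–12.6% |
| 400 v 400 | 10% v 5% | 2.9–7.3% | 0.2–0.3% | 2.7–7.1% |
| 400 v 400 | 10% v 2% | 0.0–0.2% | 0.0% | 0.0–0.2% |
| 400 v 400 | 15% v 5% | 0.0–0.4% | 0.0% | 0.0–0.4% |
| 400 v 400 | 6% v 3% | 7.6–12.1% | 1.4–1.6% | 6.2–10.8% |

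**Baseline and Week 0.** SAP 6.11.3 includes Week 0 among its timepoints. Protocol 5.2.1 lists no ANA or ESR at Week 0. SAP 6.0 sets baseline in Parts A and B as the last value before randomization, which for these tests is the screening value. In the extension, ANA and ESR are a pre-dosing assessment, and SAP 6.0 uses the last value before dosing.

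**The case against.** The strongest reply is that the harm depends on a scale that the documents do not give. If ANA is recorded as positive/negative, SAP 6.0 already calls for counts and percentages. What remains is then a conflict of wording between two sections, and a 0/1 mean at a visit is simply the proportion positive. This stands as a limit on the misranking argument. It does not supply the count of new positives among patients negative at baseline.

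Second, the table may exist. SAP 7.0 refers to table mockups in separate documents, and Addendum #1 puts the details of adverse events of special interest in another. Neither was supplied. SAP 6.11.3 also does not say that the mean is the only summary allowed. A reader might infer that no ANA conversion table will be produced. The documents do not support that; they support only that the supplied SAP text specifies none.

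Third, SAP 6.11.4 says that "Each laboratory result will be classified as low (L), normal (N), and high (H) at each visit", which could be read to include ANA. The section's own list of panels makes that reading strained.

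Fourth, other routes exist. Autoimmune disease would appear in the adverse event tables, and listings show individual results. But under Protocol 10.7.4 an abnormal laboratory value is recorded as an adverse event only if the investigator judges it clinically significant. Asymptomatic conversions could be missed there, and listings are not a comparison between arms.

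Fifth, change from baseline in laboratory data is a stated safety endpoint (SAP 3.6.3 and 3.7.2). That supports keeping a mean for ESR; it does not make a mean suitable for ANA.

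**Conclusion.** The point holds as a weakness in descriptive safety reporting. On either plausible scale, the summary prescribed for ANA does not show how many baseline-negative patients became positive, and the supplied SAP text specifies no table that does. This conclusion needs no assumption about titres or rates.

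That the mean can also rank the arms against the seroconversion rates is a secondary point. It requires ANA on a titre or similarly skewed scale. A reader might infer from the counterexample that the mean would usually mislead. The simulation does not support that: misranking ranged from 1.4% to 19.0% at B1 sizes and from 0.0% to 12.1% at B2 sizes. It was near zero in B2 when the rates differed widely. The proportion misranks too, by chance (up to 11.4% in B1 and 1.6% in B2), though less often.

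Two other inferences go too far. Exclusion 11 permits ANA-positive patients at baseline, but the documents do not show that any were enrolled. The Week 0 entry does not leave baseline undefined, because SAP 6.0 settles it; the entry is an editorial slip. No primary analysis, alpha, power or event count is affected.

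**What to change.** In SAP 6.11.3:

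1. State the ANA reporting scale and the cut-off for positivity.
2. Replace mean change for ANA with n/N (%) of baseline-negative patients who become positive, by visit and at any time.
3. Add a baseline-to-worst shift table for ANA, using titre categories if titres are reported.
4. Present these by arm in Parts A and B, and as a single group in the open-label extension, which has no comparison arm.
5. Keep mean change for ESR.
6. Refer to the SAP 6.0 baseline definitions, and remove Week 0 from the ANA and ESR timepoints for Parts A and B.

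Confidence intervals for the between-arm difference and a category for fourfold titre rises are optional. If a mockup already contains such a table, 6.11.3 should refer to it.

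The cost is SAP wording and one extra table shell. No new samples or visits are needed.

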6.11.4 Laboratory Parameters

Clinical laboratory parameters for LDH, CBC, serum chemistry and urinalysis will be summarized descriptively for Part A, open-label extension of Part A, and Part B (Safety Population). Mean and Draft v3.2 (25 May 2016)

mean change from baseline values will be presented at each study visit. Change from baseline will be calculated as the post-baseline measurement minus the baseline measurement. If either the baseline or post-baseline value is missing, the observation will not be included in the change from baseline summary.

Each laboratory result will be classified as low (L), normal (N), and high (H) at each visit according to the laboratory-supplied normal range. The shift from baseline will be presented for each post-baseline visit for Part A, open-label extension of Part A, and Part B. In addition, for Part B, toxicity grade of lab result will be presented in a shift table for each post-baseline visit for the change from baseline.

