5.2.2 Assessments at Weeks 2, 4, 6, and 8 (\pm 3 days)

At the specified visit, the following procedures will be performed. *Note: Subjects with recurrent disease may, under certain conditions, continue to receive study medications. See Section 7.2.4 for details.*

- Record adverse events
- CBC, serum chemistry, urinalysis
- Record concomitant medications
- Seviprotimut-L or placebo administration

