5.2.4 Assessments at Month 3 (\pm 7 days)

At the specified visit, the following procedures will be performed. *Note: Subjects with recurrent disease may, under certain conditions, continue to receive study medications. See Section 7.2.4 for details.*

- Record concomitant medications
- Record adverse events
- Physical examination (including weight, vital signs, and ECOG performance status)

- LDH, CBC, serum chemistry, urinalysis
- ECG (Part A only)
- Biomarker Panel (Part B only)
- Seviprothymut-L or placebo administration

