10 ASSESSMENT OF SAFETY

Safety will be assessed throughout the study by a physician, physician designate, or nursing staff. Measurements used to evaluate safety will include history, physical examination, vital signs (blood pressure, heart rate, respiratory rate, and temperature), clinical laboratory tests (hematology and clinical chemistry), urinalysis, 12-lead ECG, and monitoring for AEs. Safety will be assessed by physical examination, AE reports, clinical chemistry evaluation, and hematology evaluation. AEs will be graded according to the National Cancer Institute Common Terminology Criteria for Adverse Events Version 4 (NCI-CTCAE v4) [NCI, 2009].

Laboratory measurements that deviate significantly (as determined by the investigator) from previous measurements may be repeated. If warranted, additional or more frequent testing than is specified in the protocol should be done to provide adequate documentation of AEs and the resolution of AEs.

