3.6.3 Safety Endpoints

The between-arm comparison of safety endpoints for Part B1 of this study are:

- The incidence of all adverse events (AEs) reported during the study, including the seriousness, severity, and assessed relatedness to study drug
- Number and percent of patients discontinued from study drug treatment due to AEs
- Change from baseline in vital signs, laboratory data, and electrocardiograms (ECGs)

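### SAP 6.11.4 specifies laboratory summaries by visit only, so its text yields no per-arm proportion of patients who ever had a Grade 3-4 or newly abnormal value

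*SAP*

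**What the plan says.** SAP 6.11.4 plans three laboratory summaries for the safety population:

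- Continuous results: "mean change from baseline values will be presented at each study visit".
- Reference-range category: "Each laboratory result will be classified as low (L), normal (N), and high (H) at each visit", and then "The shift from baseline will be presented for each post-baseline visit".
- Part B only: "toxicity grade of lab result will be presented in a shift table for each post-baseline visit".

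The corresponding between-arm safety endpoint, in SAP 3.6.3 for B1 and in the same terms in 3.7.2 for B2, is "Change from baseline in vital signs, laboratory data, and electrocardiograms (ECGs". SAP 2.1 describes B1 as including a full safety comparison with placebo that helps decide whether B2 is justified.

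Protocol 10 lets the investigator repeat values that deviate markedly and adds that, if warranted, "additional or more frequent testing than is specified in the protocol should be done to provide adequate documentation of AEs". SAP 6.11.4 does not say how such results enter its tables.

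The nearest patient-level summaries are in SAP 6.11.1. Each subject is counted once per system organ class and preferred term, and there is a table by preferred term and maximum CTCAE grade. These cover adverse events, not laboratory values as such. SAP 7.0 places the table mock-ups in separate documents.

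**The concern.** By-visit tables answer how many patients were abnormal on a given occasion. A safety reader also needs to know how many patients in each arm were ever abnormal, and how badly. The second figure cannot be obtained by adding up visit tables, because the same patient may appear in several of them or in only one.

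When abnormalities are transient and fall at different visits, each table holds only a few of the affected patients, and an excess on vaccine can look like scattered single cases. Repeat or extra tests may carry a patient's highest grade, yet without a placement rule they may be dropped or handled inconsistently. At stake is how clearly the B1 and B2 reports show a laboratory safety difference. No efficacy inference is affected.

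**Working it through.** The documents give no rate, power or sample size for laboratory toxicity, so there is no planned figure to reproduce. The check has three parts.

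**1. Number of visit tables.** Part B post-baseline visits with CBC, chemistry and urinalysis during dosing:

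- "5.2.2 Assessments at Weeks 2, 4, 6, and 8" (Protocol 5.2.2): 4 visits.
- Month 3 (Protocol 5.2.4), listing "LDH, CBC, serum chemistry, urinalysis": 1 visit.
- Months 6, 12, 18 and 24 (Protocol 5.2.6): 4 visits.

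Total: 4 + 1 + 4 = 9. This is a minimum, because six-monthly laboratory tests after Month 24 (Protocol 5.2.8.2) and the end-of-study visit (5.2.9) add more.

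**2. Does another table fill the gap?** Under Protocol 10.7.4 a laboratory abnormality is recorded as an adverse event only if the investigator considers it clinically significant. Abnormalities associated with the disease are left out unless worse than expected. SAP 6.11.1 then counts the recorded events per patient. A Grade 3-4 value not judged significant, or a value that simply moves out of range, reaches no patient-level table named in the SAP text. Addendum #1 adds no laboratory table.

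**3. Size, for illustration.** B1 has 325 patients randomised 2:1: 325 × 2/3 ≈ 217 vaccine and 108 placebo. Assume a Grade 3-4 rate per visit of 1% on vaccine and 0.2% on placebo. These rates are assumptions; the documents give none.

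- Expected count in one visit table: 217 × 0.01 ≈ 2.2 vs 108 × 0.002 ≈ 0.2.
- Ever affected if the same patients are abnormal at every visit: 1% vs 0.2%.
- Ever affected if visits are independent: 1 − 0.99^9 = 8.6% vs 1 − 0.998^9 = 1.8%, or about 19 vs 2 patients.

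Exact power of a two-sided Fisher test at 0.05 (vaccine worse, 217 vs 108, full attendance) across that range, with the 5:1 rate ratio kept for the intermediate rows:

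| Ever affected, vaccine vs placebo | Expected patients | Power on ever-affected basis |
|---|---|---|
| 1% vs 0.2% (complete clustering) | 2.2 vs 0.2 | about 0% |
| 2% vs 0.4% | 4.3 vs 0.4 | 2% |
| 4% vs 0.8% | 8.7 vs 0.9 | 25% |
| 6% vs 1.2% | 13.0 vs 1.3 | 50% |
| 8.6% vs 1.8% (independent visits) | 18.8 vs 1.9 | 71% |

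In every row, power at any single visit is about 0% (1% vs 0.2%).

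One result needs no assumed rate. With no affected placebo patients, a single B1 visit table needs 9 affected vaccine patients to reach P ≤ 0.05 (9 vs 0 gives P = 0.032; 8 vs 0 gives P = 0.056).

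**The case against.** The case against giving this much weight has five parts.

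- **Unseen shells.** A reader might infer that no worst-value table will be produced. The documents do not support that. The shells are separate and unavailable, and may include one. The supportable statement is that 6.11.4 does not require it.
- **Adverse event route.** A reader might also infer that laboratory toxicity never appears at patient level. That is too strong: clinically significant abnormalities do, including by maximum grade. Investigators are blinded (Protocol 5.3.3), so the judgment should not differ by arm. What remains is graded values judged not significant and new out-of-range values.
- **Repeat tests.** SAP 6.11.4 refers to study and post-baseline visits without restricting them to scheduled ones. Protocol 10 makes repeats optional and ties extra testing to documenting adverse events. The gap is a missing rule; it is not an exclusion.
- **Power.** The rates are assumed, and 71% is the value under independence. Under strong clustering the worst-value table would also usually miss the excess. No test is planned at any visit, and a reader who sees all visits together could notice a repeated 2 vs 0 pattern.
- **Oversight.** The DMC monitors subject safety (Protocol 11.1), and the data are collected anyway, so the summary could be produced later.

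All five stand as limits on size and certainty. None of them supplies the missing summary in the SAP text. Producing it later would mean choosing the window and the handling of repeats after unblinding.

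**Conclusion.** The point holds as a minor one. The SAP text gives only by-visit laboratory summaries and no per-arm proportion of patients ever at Grade 3-4 or newly abnormal. The adverse event tables cover part of this, through investigator judgment. The benefit of a worst-value summary depends on how scattered the abnormalities are. At the assumed rates in B1 it ranges from nothing (about 0% against about 0%) to substantial (71% against about 0%). These percentages describe visibility in descriptive tables and are not the power of any planned test. They rest on assumed rates, full attendance and a fixed 5:1 ratio. It would go too far to conclude that by-visit tables cannot reveal a moderate toxicity that an ever-affected table would certainly show; the intermediate rows (25% and 50%) show that the gain is partial. If the shells already contain a worst-value table, the change reduces to aligning the SAP text with them.

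**What to change.** Add to SAP 6.11.4, for each laboratory parameter and by arm in the Safety Analysis Set:

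- shift from baseline to worst post-baseline CTCAE grade (Part B);
- shift from baseline to worst low and to worst high category, kept separate so that a patient with both is counted in each;
- unscheduled and repeat results included;
- one fixed on-treatment window, identical in both arms, for example first dose to 30 days after last dose, in line with the treatment-emergent window in SAP 6.11.1;
- counts, percentages, and the between-arm difference with its confidence interval.

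Keep the by-visit tables as supportive.

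The cost is a little extra programming: worst-value variables and a table per panel from data already collected, with no new visits, alpha or data. One drawback should be stated in the SAP: worst-value rates rise with the number of tests. For that reason the window must be the same in both arms, and the number of results per patient is worth showing alongside.
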